2. BACKGROUND

The successful transition to outpatient care after behavioral health inpatient services or discharge from an emergency department (ED) is critical to reducing suicide risk and deterioration of mental health due to disease. Social determinants, limited network of outpatient care providers and disease progression often impede patients from accessing outpatient care after discharge. 2018 data from The National Committee for Quality Assurance demonstrated that 27.5% of Medicare patients Health Care attended their outpatient follow up appointment after discharge from inpatient psychiatric care. The percent for Medicaid patients was slightly higher at 35.8% and privately insured patients had a show rate of 46.6%. After interviewing patients who were readmitted to Atrium Health Behavioral Health (AH BH) inpatient hospitals, it was determined that additional support in that critical period after discharge is needed to assist patients in successfully transitioning to outpatient care.

The Virtual Psychiatric Transition of Care (VPTC) program offers support and services to patients in the immediate post discharge period to minimize suicide risk, decrease avoidable ED and inpatient care, while helping patients successfully connect with an outpatient care provider to maintain long term success in disease management. The VPTC program provides a robust virtual care delivery system for patients as they transition from inpatient to outpatient care by wrapping around services and support during high-risk transition periods.

3. RATIONALE

The foundational idea for the VPTC program came from the Atrium Health Hospital at Home care model which has garnered wide acclaim and financial support in the acute care world. A behavioral health care team comprised of licensed clinicians (Behavioral Health Professionals), health coaches, a consulting psychiatric pharmacist and psychiatric providers follow patients for 45 days or more depending on patient need after their acute care encounter. Patient enrolled in the VPTC program will receive the following core components: Introduction to the patient follow-up process, psychosocial assessment, tracking and treatment recommendations for (residential movement, nutrition, sleep hygiene, stress management, pain management, perinatal/postpartum mood disorders, substance abuse), tracking and treatment recommendations for behavioral health symptoms (depression, anxiety, suicidal ideation, etc.), placement into an appropriate case management program if needed, navigation to additional psychiatric or substance use services if needed, and motivational interviewing and brief therapeutic recommendations if needed.

For patients that have attempted suicide, they will begin the VPTC program following the zero suicide pathway. The Atrium Health Behavioral Health Service Line created the ‘Zero Suicide pathway’, in 2019 for those patients identified as “high risk” for suicide when leaving inpatient units. Zero Suicide is a national movement sponsored by the 2012 National Strategy for Suicide Prevention, National Alliance for Suicide Prevention, Suicide Prevention Resource Center and the Substance Abuse and Mental Health Services Administration (SAMHSA). It is a programmatic approach to keep patients from falling through the cracks in a fragmented and disconnected healthcare system and is based on the belief that suicide is preventable, and suicide deaths are not fated. Since access to mental health services is constrained in our community, patients often fall through the cracks when transitioning between points of care.

4. SUBJECT AND SITE SELECTION

4.1. Accrual

For this study, all patients discharged that meet the inclusion criteria are eligible for analyses. Patients meeting eligibility criteria will accrue in both the intervention and usual care arms of the study.

A weekly list will be generated indicating patients discharged the prior week at any of the participating locations. The list contains inpatient and observation encounters. The list will identify discharged patients at facilities throughout the project, not just once the facility has implemented the VPTC program. For the purposes of this project, we are not enrolling towards a targeted patient accrual. We will enroll patients during a pre-determined data collection period, See Section 5.

4.2. Accrual – Subjects

Patients 18 years of age or older at time of discharge, a resident of North Carolina, reported a telephone number in the electronic health record, and discharged from a behavioral health hospital or a behavioral health unit will be considered exposed to the intervention, whereas patients seen at locations not utilizing the VPTC program will be considered exposed to usual care. Patients who are in the intervention arm will be treated by the behavioral health care team (licensed clinicians, health coaches, a psychiatric pharmacist, and psychiatric providers). Virtual visits are conducted telephonically. Each week a list of discharged patients will be received by the behavioral health care team.

Patients included in the analysis of this study must meet the inclusion\exclusion criteria. Patients will begin accruing based on the time the location goes live according to the role out schedule. The VPTC program is available to any behavioral health patient, but the evaluation is centered on the cohort of patients meeting the inclusion criteria.

4.3. Participating sites

The program has been piloted at AH Stanly as part of usual care. AH Stanly will not be included in the quantitative assessment. As part of the research design and rollout of this project, randomization will occur at the site level. CORE will randomize the facility participation order in advance of project kickoff. Site enrollment will begin with 1 facility, adding on 1 additional facility on a rolling basis in 3-month intervals, until all 7 facilities are active in using the VPTC program. Once added, sites will begin utilizing the program in their daily practice among the target patient population.

The following Atrium Health sites will be randomized for participation in this project.

- AH Kings Mountain Psychiatry
- AH BH Davidson - Fraser Fir
- AH BH Davidson - River Birch
- AH BH Charlotte - ED OBS

- AH BH Charlotte - North and South
- CMC Main 6B
- AH BH Davidson - Mountain Laurel

4.4. Inclusion\Exclusion Criteria

4.4.1. Inclusion Criteria

Eligible patients in the analyses must meet each of the following criteria:

- Residency or shelter in North Carolina
- 18 years of age or older on the day of discharge
- Access virtual care (phone/video) - having a phone number in the electronic health record
- Discharged from a behavioral health hospital or a behavioral health unit

4.4.2. Exclusion Criteria

- None

4.5. Evaluable Population

Patients included in the evaluable population for this project, will have their data inform the final outcomes assessment. All patients who meet the inclusion and exclusion criteria in both groups of the study will be assessed for the primary outcome (intent to treat).

5. OVERALL DESIGN

5.1. Variables

5.1.1. Primary Outcome Variable

The primary outcome variable is 30-day all cause non-elective acute care post discharge utilization (ED, inpatient, and observation encounters).

5.1.2. Secondary Outcome Variables

- a. Demographic characteristics (age, race, gender, insurance plan)
- b. Charlson comorbidity index score
- c. 60-day all cause non-elective acute care utilization (ED visits, observation, and inpatient encounters).
- d. 30-day behavioral health acute care utilization (ED visits, observation, and inpatient encounters).
- e. A behavioral health office visit within 7 days of discharge
- f. An avoidable ED visit within 30 days of discharge

5.1.3. Exploratory Variables

- g. Assess symptom improvement for depression
 - i. Initial- PHQ-9 total score
 - ii. Post- PHQ-9 total score
- h. Assess suicidal ideation
 - i. Initial- PHQ-9, Q9 score
 - ii. Post- PHQ-9, Q9 score

5.2. Trial Design

5.2.1. Justification for stepped wedge cluster randomized control trial

The primary aim is to assess the effectiveness of a structured multidisciplinary care plan (intervention), compared with usual care (control) on 30-day all cause non-elective acute care utilization (ED visits, observation, and inpatient encounters). The VPTC program will be delivered at the level of location or cluster, thus minimizing contamination and the risk of selection bias, if subjects were randomized at the individual level. Therefore, the unit of randomization and analysis for this study will be the cluster. Considering logistical constraints and design rigor, the intervention will be rolled out sequentially instead of at the same time. Moreover, substantial and differential cluster-effects may exist because of distinct volume and characteristics of patients in each hospital. Thus, the stepped wedge design is advantageous compared with other alternative designs.

The stepped wedge design implies a baseline period, in which no clusters are exposed to the intervention. Then, at the chosen time interval of three months, one location will be randomized to cross from the control to intervention (Figure 1). This process continues until all seven locations have crossed over to the intervention. The order of this cross over process will be randomized. We will use randomization to assign location order so that if a high or low volume location is assigned cluster 1, a high or low volume location is assigned cluster 7. The single ED location will be assigned to cluster 4. SAS Enterprise Guide version 8.2 will be used for the randomization. Allocation will be communicated only to the behavioral health team initially to prevent contamination. Locations will learn of allocation in the month preceding roll-out. Patients in included locations will be blinded to the intervention or control period.

An example of the roll out schedule

Location	August 2021	November 2021	February 2022	May 2022	August 2022	November 2022	February 2023	May 2023
Location 1	0	1	1	1	1	1	1	1
Location 2	0	0	1	1	1	1	1	1
Location 3	0	0	0	1	1	1	1	1
Location 4	0	0	0	0	1	1	1	1
Location 5	0	0	0	0	0	1	1	1
Location 6	0	0	0	0	0	0	1	1
Location 7	0	0	0	0	0	0	0	1

1=Virtual Psychiatric Transition of Care Program; 0=Usual Care

5.2.2. Virtual Psychiatric Transition of Care Program

5.2.2.1. Zero Suicide Pathway

Depending on the patient's reason for admission, patients may start the VPTC program in the zero suicide pathway. Patients that meet criteria for this higher level of care will have attempted suicide. Patients are identified from the C-SSRS screening tool along with referrals from the treatment team and treating psychiatrist. Identified patients are enrolled a day or two prior to discharge and then contacted within 24 hours of discharge, to assess for suicidality and self-harm and to review safety plans and discharge instructions. Patients are contacted daily, to every few days until they no longer need the higher-level of outreach and will be transferred to the VPTC pathway. VPTC clinicians will continue to outreach with the patient for the remaining time in the VPTC program.

5.2.2.2. VPTC Pathway

If a patient has not attempted suicide as the reason for admission, VPTC clinicians will begin outreach with the patient within the first 24-72 hours after discharge. The first outreach with the patient will be completed by a licensed clinician who will complete a brief psychosocial assessment with the patient. After the initial outreach is completed a health coach will then reach out to the patient to set a weekly schedule. The weekly outreach with the VPTC health coach will be patient centered and patient specific. These outreach will help support patients through goal setting/treatment plans, medication support, linkage and support to community resources, and safety planning. These outreach will also help patients identify any barriers they may have in attending their follow up care with their outpatient community providers. Throughout the outreach at any point and time if a patient has a question or concern about their medication the VPTC licensed practicing nurse can contact the patient to help address those needs. At each outreach patient's safety is also assessed. At any point in the outreach if a patient endorses any safety concerns that patient will be assessed by a licensed qualified clinician to identify those safety concerns and create a safety plan with the patient.

If the patient is scheduled with a VPTC psychiatric provider for a hospital follow-up appointment, an LPN (Licensed Practical Nurse) will outreach to the patient before that visit to complete the nursing intake. The patient will then have their hospital follow up visit either with their community provider, or the VPTC psychiatric provider. The VPTC psychiatric provider will review medications that the patient started on the inpatient unit or emergency department and provide any further education, adjustments, and support. The provider is able to order the medications. The VPTC program will also have support from a psychiatric provider through weekly treatment team huddles to help support patients and identify any barriers they may be facing.

There may be cases where patients are eligible to enroll in full case management programs based on their insurance or other criteria. In these situations, the VPTC team will coordinate a care transition and the patient will be considered to have completed the program. For example, if a patient has Medicaid through a local management entity, a managed care organization providing local behavioral health care, and meets certain criteria, the patient will not require services from the VPTC team as they would be duplicative.

5.3. Patient Graduation from the VPTC Program

- Reached max benefit as deemed by the behavioral health care team
- Unable to connect: 4 calls attempted over 12 days
- Transition to lower level of care
 - Patients who transition to a primary care clinic
- Transition to higher level of care
 - Psychiatry/Treatment Program
 - Readmission to an Inpatient Facility
- Declined or no longer interested in services
- Death

5.4. Continuation of the Intervention

Patients may continue enrolling in the VPTC program after the study period has ended.

6. QUALITATIVE REVIEW

A qualitative evaluation will be conducted among the care team and patients at the pilot location. This evaluation aims to evaluate the implementation of the psychiatric virtual transition of care program and the nature of the targeted patient population. The qualitative data collection for this study will be guided by the Consolidated Framework for Implementation Research (CFIR). The CFIR incorporates several established implementation theories into a common framework. Composed of a menu of 39 constructs that fall into 5 domains (intervention characteristics, outer setting, inner setting, characteristics of individual, and process), the CFIR is used to design, guide, and evaluate health care delivery interventions by identifying potential or existing barriers and facilitators to implementation (Damschroder et al. 2009). Through the aggregation of corroborated constructs, the CFIR promotes a systematic and consistent use of implementation measures, which help render study findings intelligible and generalizable. The framework is well-suited to projects like the VPTC program as it allows for complex theory-building and cross-study comparisons using a common set of constructs while obviating the need to use multiple implementation frameworks.

Semi-structured CFIR-guided interviews will be conducted with 12 VPTC patients/care takers and 12 VPTC team members. This sample size was arrived at after considering the project's narrow study aim (Malterud et al., 2016). Clinician interviews will include a diversity of frontline staff, including, but not limited to, nurses, health coaches, psychiatrists, and discharge planners.

Patient-interviewees will have been enrolled in the VPTC program and be targeted using a convenience sample, a non-probability sampling strategy commonly used for studying reclusive and reluctant populations (Bernard, 2017; Guest et al., 2006). A VPTC team member will reach out to the patient and ask if contact can be made to discuss their thoughts on the VPTC program. A researcher will call to follow-up with and schedule an interview with the patient. During recruitment calls, potential patient-interviewees will be assured that their receiving of care is not in any way contingent on consenting to an interview. This assertion will be reaffirmed by the interviewer before the beginning of interviews. Patients that complete an interview will be compensated for their time with a \$25 Clincard.

Clinician-interviewees will be recruited through snowball sampling: The VPTC coordinator will identify and refer clinicians and other relevant staff for interviews, these interviewees will in turn be asked to identify other potential respondents. A researcher will send up to two weekly emails to introduce clinicians to the qualitative review and encourage them to contact us to schedule an interview. A researchers will schedule an appointment with those who reply to the email and are interested. All interviews will be conducted via telephone and will be audio recorded.

The recorded interviews will be de-identified and then parsed and analyzed using ATLAS.ti 9. The analytical approach will be inductive—building theory on patterns found in the data—as such analyses are typically well-suited for exploratory examinations of novel or under-studied social phenomena. Coding will begin at the question-level, allowing the qualitative team to compare all interviewee answers to a specific question. Next, a vertical analysis across interviews will be conducted using the constant comparative method, a “scrutiny-based technique” (Ryan and Bernard, 2003: 101) foundational to grounded theory, an approach in which theory building is based in empirical analysis rather than deductive inference. Using this comparative method, codes will be produced inductively and iteratively, as early codes often have a contingent and provisional quality and must be delineated and refined through a continual comparison with preceding and subsequent data (Boeije, 2002). During these vertical readings, codes will be used to paraphrase and summarize passages.

Themes will be developed using the constant comparative method, which provides a framework to understand the commonalities and differences within and among interviews, as the method is also a method of identifying contrasts. (Bradley, Curry & Devers 2007). Themes will be inferred from particular, reoccurring instances—through the repeated parsing and partitioned of interview data according to CFIR constructs and the relevance to our research questions. Once barriers and facilitators of implementation have been identified using the CFIR framework, recommendation will be drafted to optimize implementation of the VPTC program.

The most immediate risk of the aforementioned data collection procedures to interviewees is the potential for embarrassment, should their unredacted interview data be shared. Several measures will be put in place to protect the identity and confidentiality of interviewees: recordings of the interviews will be stored on a password-protected computer accessible only to pertinent project staff; transcriptions of the interviews will be de-identified, i.e. the names of interviewees, employers, and care providers will be redacted; and interview quotes used in subsequent presentations, reports, and publications will be anonymized.

7. DATA COLLECTION AND REPORTING

Patient demographics, Charlson comorbidity score, and utilization will be obtained from the electronic medical record and billing systems. Data from the initial assessment and follow-up contacts will be stored in HealtheCare, a care management platform in Cerner. Data will be retrieved by an application specialist on the research team. Data may be retrieved retrospective to a patient’s completion of the intervention or

usual care arm of the study. A participation rate can be generated from the count of patients enrolled in the VBHI program over the count of patients meeting the inclusion criteria.

A bi-monthly report will be produced for the intervention arm. The report will be by primary care practice and overall showing the prior 2 weeks of activity.

- Count of patients meeting the inclusion criteria
- Count of patients with a HealtheCare account
- Count of patients enrolled in the VBHI program
- Patient list with their enrollment status in HealtheCare

A monthly report will be produced for the intervention arm. The report will be by primary care practice and overall. Report to be generated 2 weeks after the end of the month showing the prior month of activity.

- Count of patients meeting the inclusion criteria
- Count of patients with a HealtheCare account
- Count of patients enrolled in the VBHI program
- Patient list with their enrollment status in HealtheCare

7.1. Sample Size Analysis

Calculations of sample size were based on primary analysis of 30-day non-elective acute care utilization on a binary group. Our preliminary data shows that average unique patients in each hospital (cluster size) per three months ranged from 159 to 300, we expected an enrollment rate of 40%. Thus, the average effective cluster size is 96 with a standard deviation of 15. Conservatively, we would at least expect an average cluster size of 81. With the assumption of detecting a change from 20% in the control period to 14% in the intervention period for 30-day non-elective acute care utilization, a mean cluster size of 81 with seven clusters and seven steps (8 time periods inclusive of a control period) would achieve a power of 0.89 if intra-class correlation coefficients (ICC)=0.20 and two-side $\alpha=0.05$. Holding other parameters constant, the larger ICC is, the higher the power we will obtain. The coefficient of variation (CV) of sample size is approximately 0.15. To account for this varying cluster size, we inflated the number of patients by 10% resulting in an average cluster size of 89 patients per three months, resulting in a sample size of 2,495 patients among the intervention group and 4,990 patients overall inclusive of our control population. In this pragmatic trial, those assigned to the intervention but did not enroll in VPTC during the intervention period (around 60%) would also be counted in the intervention arm. It is within our expectation that intervention arm eventually has smaller reduction in 30-day non-elective acute care utilization (i.e. $0.4*0.14 + 0.6*0.20 = 17.6\%$, difference=2.4%). However, we still ensure a power above 0.80 as long as over 2,495 patients actually received VPTC. The power was calculated by using the PASS 15.

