	
• Navigation to additional psychiatric or substance use services, if needed• Motivational interviewing and brief therapeutic recommendations, if needed
Statistical Analysis	Analyses will include all patients identified as having been discharged and meeting the inclusion criteria. Baseline comparisons of the intervention and usual care groups will be made using univariate analyses. The primary analysis will be conducted using generalized linear mixed models with fixed effects for intervention, and intervention multiply by the time, accounting for the cluster randomized trial design with a random cluster (hospitals) or time (steps) effect. Results will be presented with odds ratios and 95% confidence intervals.

LIST OF ABBREVIATIONS

BHI	Behavioral Health Integration
CORE	Center for Outcomes Research and Evaluation
C-SSRS	Columbia – Suicide Severity Rating Scale
EDW	Enterprise Data Warehouse
VPTC	Virtual Psychiatric Transition of Care
NC	North Carolina
PHI	Private Health Information
PHQ-2	Patient Health Questionnaire - Screener for Depressive Disorders
PHQ-9	Patient Health Questionnaire – Screener for Severity of Depression
SOP	Standard Operating Procedures

TABLE OF CONTENTS

1.1.	Hypothesis.....	8
1.2.	Primary Objective	8
1.3.	Secondary Objectives	8
1.4.	Exploratory Analyses	8
2.	BACKGROUND	9
3.	RATIONALE	9
4.	SUBJECT AND SITE SELECTION	10
4.1.	Accrual.....	10
4.2.	Accrual – Subjects	10
4.3.	Participating sites	10
4.4.	Inclusion\Exclusion Criteria	11
4.4.1.	Inclusion Criteria	11
4.4.2.	Exclusion Criteria	11
4.5.	Evaluable Population	11
5.	OVERALL DESIGN.....	11
5.1.	Variables	11
5.1.1.	Primary Outcome Variable.....	11
5.1.2.	Secondary Outcome Variables	11
5.1.3.	Exploratory Variables	12
5.2.	Trial Design	12
5.2.1.	Justification for stepped wedge cluster randomized control trial	12
5.2.2.	Virtual Psychiatric Transition of Care Program	13
5.2.2.1.	Zero Suicide Pathway	13
5.2.2.2.	VPTC Pathway	13
5.3.	Patient Graduation from the VPTC Program	14
5.4.	Continuation of the Intervention	14
6.	QUALITATIVE REVIEW	14
7.	DATA COLLECTION AND REPORTING.....	15
7.1.	Sample Size Analysis	16
7.2.	Statistical analysis	16
7.3.	Missing Data	17
7.4.	Training	17
7.5.	Data Collection Dates.....	17

8. INTERVENTION PLAN.....	18
8.1. Behavioral Health Professional Assessments.....	18
8.2. Follow-up Assessments.....	18
8.3. Psychiatric Virtual Appointments.....	18
9. STUDY GOVERNANCE	19
10. SAFETY RISKS AND REPORTING.....	19

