7.2. Statistical analysis

Distributions of baseline characteristics for locations and patients will be compared between the intervention or control periods to assess effectiveness of the randomization, and statistical or clinical differences will be adjusted in sensitivity analyses. All analyses for treatment and control periods comparisons will use an intention-to-treat approach and results will be reported used the CONSORT extension to cluster randomized trials.

The primary outcome for this study is 30-day all cause non-elective acute care utilization. Characteristics of the locations and individuals will be summarized by levels of randomization steps, locations, and individuals. The count, rates and 95% confidence intervals of 30-day non-elective acute

care utilization in the control period will be presented and compared with that in the treatment period. The primary analysis will be conducted using generalized linear mixed models with fixed effects for intervention, and intervention multiply by the time, accounting for the cluster randomized trial design with a random cluster (hospitals) or time (steps) effect. We will estimate and report the intra class correlation coefficients for all outcome measures to assess assumptions for sample size analyses and for future investigations using similar designs and outcomes. The primary analyses will follow the intention to treat principle with an additional per protocol analysis including those who actually used VPTC. The secondary analyses will include within cluster comparisons of intervention and control periods (not adjusting for any confounding effect of time), as well as comparisons of a series of (unbalanced) quasi-parallel cluster trials between those enrolled and unenrolled clusters at each intervention enrollment period. The same analyses plan will also be applied to secondary outcomes.

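### The power of 0.89 matches a stepped-wedge model with one constant intervention effect, but the primary model also fits intervention × time, and no power is given for that model

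*Combined protocol and SAP*

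**What the plan says.** Section 7.1 ties its calculation to the primary analysis of 30-day non-elective acute care utilization. The target is "detecting a change from 20% in the control period to 14% in the intervention period", with 81 patients per location-quarter, seven locations, eight periods and two-sided alpha 0.05. On those inputs it "would achieve a power of 0.89 if intra-class correlation coefficients (ICC)=0.20". The software is named (PASS 15), but no formula or model is given and no interaction is mentioned.

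Section 7.2 defines the primary analysis as "generalized linear mixed models with fixed effects for intervention, and intervention multiply by the time", with a random effect for cluster or for step. The Statistical Analysis entry of the synopsis repeats "fixed effects for intervention, and intervention multiply by the time" and promises odds ratios with 95% confidence intervals. Neither place lists a main effect of time, says whether time means calendar quarter or time since go-live, says whether it is linear or categorical, or names the coefficient, average or joint test that decides the trial.

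**The concern.** In a stepped wedge, an intervention × time term is strongly collinear with the intervention indicator, because intervention accumulates as time passes. Adding the term changes what the intervention coefficient means and can greatly inflate its standard error. With the term in the model there is also no single intervention odds ratio unless a contrast is named.

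If 0.89 belongs to a model without the term, the plan gives no power for its stated primary analysis. A non-significant intervention odds ratio could then reflect the added term and be misread as no effect. Leaving the contrast open would also allow it to be chosen after the data are seen.

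This is separate from the dilution to 17.6% described in Section 7.1, because the comparisons below keep the full 6-point effect. It is also separate from the missing time main effect, because the mismatch remains when period effects are added.

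**Working it through.** **Inputs.** From Section 7.1: 20% v 14% (difference 0.06), ICC 0.20, m = 81 per location-quarter (the cluster size is defined as "average unique patients in each hospital (cluster size) per three months"), 7 locations, 8 periods, two-sided 0.05. The schedule is the one in Section 5.2.1, which has 28 intervention location-quarters. Total variance = 0.20 × 0.80 = 0.16. Between-location variance τ² = 0.20 × 0.16 = 0.032. Residual variance of a location-quarter mean σ² = 0.128/81 = 0.00158.

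**Step 1: reproduce 0.89.** With random location, fixed periods and one constant effect,

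Var = Iσ²(σ² + Tτ²) / [(IU − W)σ² + (U² + ITU − TW − IV)τ²],

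where I = 7, T = 8, U = 28 (intervention cells), W = 140 (sum of squared period totals) and V = 140 (sum of squared location totals).

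- Numerator: 7 × 0.00158 × (0.00158 + 0.256) = 0.002849
- Denominator: 56 × 0.00158 + 252 × 0.032 = 8.1525
- Var = 0.0003495, SE = 0.0187
- 0.06/0.0187 = 3.21; power = Φ(3.21 − 1.96) = 0.894

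This matches the printed 0.89. Using a pooled variance gives 0.93, and reading 81 as the total per location over all periods gives 0.21. Neither matches.

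**Step 2: add intervention × linear calendar time, keeping period effects and a true constant 6-point effect.** By symmetry of the schedule, the effect at period t (coded 0–7) has variance Var(3.5) + (t − 3.5)² × Var(slope). Generalized least squares gives SE 0.0187 at t = 3.5 and 0.0401 at t = 0, so Var(slope) = (0.0401² − 0.0187²)/12.25 ≈ 0.000103.

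- Intervention coefficient, time coded 0–7 (t = 0): SE 0.0401, power 0.32
- Intervention coefficient, time coded 1–8 (t = −1 on the 0–7 scale): SE = √(0.00035 + 20.25 × 0.000103) = 0.0493, power 0.23
- Average over the 28 intervention cells (mean period 140/28 = 5): SE = √(0.00035 + 2.25 × 0.000103) = 0.0241, power 0.70

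The coefficient's power changes merely with where time is set to zero.

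**Step 3: other contrasts with period effects fitted (m = 81).**

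| Interaction and contrast | Power |
|---|---|
| Linear calendar time, mid-trial effect | 0.89 |
| Linear time since go-live, first-quarter effect | 0.885 |
| Linear time since go-live, average over 28 cells | 0.66 |
| Linear time since go-live, equal average over exposure quarters 1–7 | 0.51 |
| Either linear form, joint 2-df test (non-centrality 3.21² = 10.3) | 0.83 |
| Categorical calendar time, averages | 0.81–0.88 |
| Categorical time since go-live, averages | 0.49–0.66 |

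**Step 4: the terms exactly as listed (random location, no time main effect).** The intervention coefficient with linear calendar time has SE 0.0287 and power 0.55 (0.44 if time is coded 1–8). Averages are 0.985–0.998 and joint tests 0.97–0.995. These high figures assume no secular trend.

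**Step 5: random location plus random step** (step variance is not in the plan; assumed 0.0005–0.002). The calendar-time coefficient is 0.28–0.45. With a linear interaction, averages are mostly 0.87–0.96 (lowest 0.79, time since go-live), and joint tests are 0.87–0.94.

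**Scale.** Steps 1–5 use large-sample z tests on the risk-difference scale. A logistic simulation with fixed location and period effects gave 0.84–0.86 for the constant effect, 0.29 for the calendar-time coefficient, and 0.67–0.68 (calendar) or 0.64–0.65 (go-live) for the averages. The ordering is the same, and part of the shortfall from 0.89 is scale.

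**The case against.** A reader might infer that most versions of the primary analysis fall well below 0.89. The documents do not support that. The lowest figures need fixed period effects, which Section 7.2 does not list, together with a linear interaction, which it does not state. On the listed terms alone, averages and joint tests exceed 0.89, and with the random step effect that the text names, many are close to or above it. What stands on the other side is that high power without a time main effect requires no secular trend. Section 7.2 also implies that the primary analysis adjusts for time, because it sets the secondary within-cluster comparison apart as the one without such adjustment.

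A reader might also infer that the trial itself is underpowered for a 6-point effect because of the interaction. That does not follow either. The 81 counts enrolled patients at 40%, whereas the intention-to-treat analysis uses all eligible patients, about 81/0.4 = 202 per location-quarter. At 202 and the full 6 points, with period effects and a linear interaction, the averages have power 0.96–0.98 and the joint test 0.997; the calendar-time coefficient stays at 0.66. But Section 7.1 itself expects only 2.4 points in that population, where even the constant-effect model has about 0.53 at 202.

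Finally, the printed arithmetic is not wrong. The figure reproduces; the fault is that it is not shown to belong to the stated primary model.

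**Conclusion.** The point holds as a mismatch between the power statement and the primary model. The 0.89 is the power of a constant-effect stepped-wedge analysis, as inferred from a close match. The stated primary analysis has an extra term, and its power was not given.

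At 20% v 14%, m = 81 and ICC 0.20, with period effects and a linear interaction, the main readings run from about 0.23 to 0.89 depending on choices the plan leaves open. The most exposed is the intervention coefficient with linear calendar time, which is 0.23–0.32 with period effects and 0.44–0.55 for the model as listed. At the plan's inflated size ("resulting in an average cluster size of 89 patients per three months") the constant-effect power is 0.92 and the linear averages are 0.70–0.74, so the inflation does not close the gap.

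These figures assume a truly constant effect and large-sample tests with only seven locations. The 0.66 and 0.70 hold only for linear coding at m = 81 and should not be printed as replacements without recalculation.

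**What to change.** In Section 7.2 and the synopsis, state three things: the main effect of time (quarter), the coding of time in the interaction (calendar or since go-live, linear or categorical), and the single contrast that is the primary test.

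In Section 7.1, do one of the following:

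- Replace 0.89 with the power of that contrast, calculated at the cell size and effect of the intention-to-treat analysis.
- Label 0.89 as applying only to a model with location, quarter and one constant effect at m = 81 and 20% v 14%.

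If the sponsor makes the constant-effect test primary, keep intervention × time as a pre-specified secondary analysis and state the downside. With period effects at ICC 0.20 and m = 81, that single estimate weights exposure quarters 1–7 as 0.66, 0.39, 0.18, 0.03, −0.07, −0.11 and −0.08. If benefit built up as 2, 4 and then 6 points, it would estimate 0.66 × 2 + 0.39 × 4 + (0.18 + 0.03 − 0.07 − 0.11 − 0.08) × 6 ≈ 2.6 points, against an equally weighted mean of (2 + 4 + 5 × 6)/7 = 5.1.

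The cost is wording in three places and one recalculation, with no extra patients or data. The price is either a less favourable printed power or a primary estimate that can misrepresent the average effect if benefit changes with time since go-live.
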